Psychological moderators. Further, participants high in internalized weight bias (IWB) and neuroticism were more likely to view the negative feedback as reflecting weight discrimination and to report more negative emotions, whereas participants high in self-compassion and conscientiousness demonstrated the opposite pattern. Findings support Aim 1 by demonstrating effects of weight discrimination on negative emotions and self-regulation and Aim 2 by identifying psychological moderators.

Pilot Study 3: Cognitive, Affective, and Behavioral Correlates of Expectations of Rejection. This lab study identified individual differences associated with expectations of rejection during a novel social interaction and the implications of those expectations for psychological and behavioral outcomes. Before completing a task with a partner (a member of the study team), adults with obesity (N=111) reported the extent to which they thought they would be accepted vs. rejected by their partner. Participants who anticipated rejection by their partner reported more distress and anxiety. Expectations of rejection were also associated with social withdrawal, indicated by participants choosing to work by themselves to avoid further social interaction.

Psychological moderators. Participants high in internalized weight bias and neuroticism reported higher expectations of rejection, more distress and anxiety, and greater social withdrawal. In contrast, participants high in self-compassion demonstrated the opposite pattern. These findings demonstrate support for Aim 2.

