Intentions for weight control behavior. Using the same health behaviors assessed for self-efficacy, we will also assess intentions for weight control behavior. Participants will be asked to rate the extent to which they intend to engage in each behavior over the next six months.¹⁰⁵ Each item will be rated on an 8-point scale (0=strongly disagree to 7=strongly agree). Items will be averaged to create a composite score.

Measures to assess physiological mechanisms.

Cortisol reactivity. We will measure cortisol secretion via saliva (passive drool) at three timepoints during the session: baseline, 20 minutes post-manipulation (to assess reactions to the manipulation), and 60 minutes post-manipulation (to assess recovery).¹⁰⁶ As in previous research,¹⁰⁶ participants will be asked to swish their mouths with water 2-3 times before the final sample is collected to avoid altering cortisol levels. Within 2 hours of collection, saliva samples will be frozen at -20°C. As in our previous work,⁴⁸ samples will be analyzed in duplicate with immunoassays. Participants will be instructed to refrain from eating, drinking, smoking, or exercising for 1 hour before the session. To reduce diurnal cortisol variability, sessions will be conducted between 1:00 and 7:00 p.m. During the session, we will assess factors that could potentially affect assay results (e.g., consumption of food, alcohol, nicotine within the past 12 hours; presence of oral diseases or injury; current medications), so that we can control for them in analyses if needed.

Measures to assess moderators (Table 2). Moderators will be assessed with an online survey completed at least one week before the experimental session. We will use reliable and well-validated measures to assess all psychological moderators. Internalized weight bias will be assessed with the 11-item Modified Weight Bias Internalization Scale.⁷⁹ Self-compassion will be assessed with the 26-item Self-Compassion Scale.⁸³ The 60-item Big Five Inventory-2⁸² will be used to assess the five core personality domains (extraversion, agreeableness, conscientiousness, neuroticism, and openness). To mask the study's focus, the survey will include other measures unrelated to weight stigma (e.g., emotion

PROTOCOL TITLE: Decision Making Study

regulation),¹⁰⁷ plus demographic characteristics (e.g., education, biological sex) and health status (e.g., physical and mental health status, past medical history).

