Participants will be thanked for their participation and given the written debriefing form. The debriefing form will provide a more detailed version of the verbal debriefing by outlining the study purpose and rationale underlying the current study. After receiving the verbal and written debriefing, participants will be given an opportunity to discuss the study with the research assistant and ask questions about the procedures and study goals. Participants will also be provided with several suggested readings if they are interested in learning more about weight discrimination and health, efforts that will be taken to protect their confidentiality, and a list of psychological support resources. The form will include contact information for the PI ([name]) and the FSU human subjects committee should participants have any additional questions or concerns about the study.

Participants will be instructed to contact the PI if they would like to receive a copy of the

PROTOCOL TITLE: Decision Making Study

study results.

Source Records: Please see attached documents for all surveys that will be used to collect data about participants (i.e., screening survey, baseline survey, lab survey).

Describe what data will be collected during the study and how that data will be obtained.

Outcome measures include cognitive (self-regulation); affective (emotional states); behavioral (social withdrawal, comfort eating); and physiological (cortisol secretion as indicated via saliva) responses to experimentally manipulated weight discrimination. Measures will be assessed with experimenter-administered and self-administered survey questions, computer-based tasks, a saliva sample, and a faux taste test. Please see previous description of outcomes for more detail.

Proposed psychological and demographic moderating variables will be assessed in the screening survey and baseline survey.

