17.0 Data Management and Confidentiality

Statistical Design, Power, and Analysis Plan

We designed this study to have very high power for the main effects of weight discrimination (Aim 1) and to ensure sufficient sensitivity for moderation effects of psychological (Aim 2) and demographic variables (Aim 3).

➤ **Aim 1: Identify early-stage cognitive, affective, behavioral, and physiological mechanisms activated by experimentally manipulated weight discrimination.** We hypothesize that, relative to participants in the control condition(s), participants in the weight discrimination (experimental) condition (vs. control) will display more impaired self-regulation, higher negative emotion, lower positive emotion, more social withdrawal and comfort eating, lower self-efficacy and intentions for engaging in weight control behavior, and increased cortisol secretion.

Aim 1 power and analysis. Nine outcomes are assessed for the study (Table 1), hence we adopt a conservative Bonferroni adjustment when evaluating the primary hypothesis and use significance level $\alpha = 0.005$ to maintain familywise Type I error rate of 0.05. We assumed conservative effect size estimates, which were among the smallest observed in our pilot data.⁴⁸ We plan to recruit 160 subjects per condition for the study, which yields 90% power ($\alpha = 0.005$) to detect the medium Cohen's $d = 0.50$ between the control and experimental conditions.

Aim 1 analyses will use unadjusted ANOVA followed by analysis of covariance and multiple regression methods that permit adjustment for age and other baseline characteristics that may exhibit imbalance across experimental conditions. To analyze effects of the manipulation on cortisol secretion (assessed at 3 timepoints), we will calculate the area under the curve (AUC) with respect to ground (AUCg).¹²⁰ For all Aims, residual diagnostics will assess model assumptions (e.g., normality, homogeneity) and responses will be transformed if necessary. Effect of experimental weight discrimination will be reported for both unadjusted and adjusted analyses.

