➤ **Aim 2: Identify psychological variables that moderate effects of weight discrimination.** We hypothesize that the effect of weight discrimination (vs. control) will be stronger for individuals who score higher on certain psychological variables (i.e., internalized weight bias, neuroticism) and weaker for individuals who score higher on other variables (i.e., self-compassion, conscientiousness; See Table 2). In other words, possessing some traits will be protective, while possessing other traits may render individuals more vulnerable to the harmful effects of weight discrimination.

Aim 2 power and analysis. The very high power of these designs for the primary hypotheses of Aim 1 ensures sufficient power for Aim 2 and additional analyses.

PROTOCOL TITLE: Decision Making Study

Statistical analysis will use multiple regression with condition assignment, the moderator, and their interaction as predictors and focus on interpretation of the coefficient for the interaction.¹²¹ With a continuous moderator, the coefficient for the interaction is the difference in the slope coefficients associated with the moderator in each of the treatment groups. Because these slopes are proportional to the correlation between the moderator and outcome in each group, respectively, the test of no moderation is equivalent to the test of equal correlation between moderator and outcome in all groups. Using Fisher's z transform of the correlations to approximate normality, The study (with 160 subjects in each of two conditions) provides 90% [80%] power (2-sided, $\alpha = 0.05$) to detect the change in correlation between moderator and outcome from 0.65 to 0.39 [0.43] associated with treatment assignment.¹²² Additional statistical analyses will adjust for baseline characteristics by including these as additional predictors in the model; estimated moderation effects will be reported for both unadjusted and adjusted analyses.

➤ **Aim 3: Identify demographic characteristics that moderate effects of weight discrimination.** We will conduct exploratory analyses to assess whether the negative effects of weight discrimination are moderated by age, sex/gender, race, and ethnicity.

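### Aim 1 chooses covariates other than age by possible baseline imbalance and does not name the result judged at 0.005; a fixed set of pre-session predictors would be a cheap, modest improvement.

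*Combined protocol and SAP*

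**What the plan says.** Section 17.0 sets a per-outcome level of 0.005 for nine outcomes, to hold the familywise error rate at 0.05. It then states: "Aim 1 analyses will use unadjusted ANOVA followed by analysis of covariance and multiple regression methods". These later models "permit adjustment for age and other baseline characteristics that may exhibit imbalance across experimental conditions". On reporting: "Effect of experimental weight discrimination will be reported for both unadjusted and adjusted analyses". There is no covariate list, no imbalance threshold and no statement of which result is decisive, here or elsewhere.

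Three features lean towards the unadjusted ANOVA:
- It comes first.
- The power statement rests on a plain Cohen's d of 0.50 "between the control and experimental conditions".
- Aim 2 treats its adjusted models as extras: "Additional statistical analyses will adjust for baseline characteristics by including these as additional predictors in the model".

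The likely predictors are already in hand. Section 4.0 says: "Moderators will be assessed with an online survey completed at least one week before the experimental session". Section 6.0 says: "Proposed psychological and demographic moderating variables will be assessed in the screening survey and baseline survey". Section 3.0 (Pilot Study 3) reports: "Participants high in internalized weight bias and neuroticism reported higher expectations of rejection, more distress and anxiety, and greater social withdrawal".

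**The concern.** In a randomised experiment, a baseline difference between conditions is chance. Its size says little about whether adjusting for that variable will sharpen the treatment comparison; what matters is how well the variable predicts the outcome. An imbalance criterion therefore selects on the wrong property and makes the model depend on the random draw.

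Two consequences follow, depending on which result decides. If it is the unadjusted ANOVA, precision available from data already collected is not used in the confirmatory test. If it is the imbalance-driven model, most of that precision is still lost in the scenarios simulated below. In a small share of trials the two reported results would fall on opposite sides of 0.005, and the plan has no tie-break.

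**Working it through.** **Inputs.** From Section 17.0: 160 per condition, per-outcome alpha 0.005, d = 0.50, stated power 90%. Sidedness is not stated for Aim 1; two-sided is assumed, as in Aim 2. Assumed, because the documents give no values: a correlation r between the covariate set and the outcome of 0.1 to 0.52, and an illustrative smaller effect of d = 0.40.

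**The plan's own figure.** Unadjusted noncentrality is d × √(160/2) = 0.50 × √80 = 4.47 on 318 degrees of freedom, against a critical value of 2.83. Power is 94.9%, not 90%. The stated 90% is matched only with about 15% attrition (136 per arm gives 90.1%), which the plan does not mention. The difference is on the safe side and is separate from this point.

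**Fixed adjustment.** Noncentrality becomes d × √80 / √(1 − r²) on 314 degrees of freedom with four covariates. Chance imbalance in those covariates inflates the variance by (320 − 3)/(320 − 3 − 4) = 317/313 = 1.013, about 1.3%. The net columns include this cost.

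| r | d = 0.40, before cost | d = 0.40, net | d = 0.50, before cost | d = 0.50, net |
|---|---|---|---|---|
| unadjusted | 77.3% | – | 94.9% | – |
| 0 | – | 76.6% | – | 94.6% |
| 0.1 | 77.8% | 77.1% | 95.2% | 94.9% |
| 0.2 | 79.4% | 78.8% | 95.8% | 95.5% |
| 0.3 | 82.1% | 81.5% | 96.8% | 96.6% |
| 0.52 | 91.2% | 90.8% | 99.2% | 99.1% |

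Break-even is R² of about 0.013, that is r of about 0.11. A 20,000-run regression simulation with four covariates agrees at d = 0.40: 76.4%, 77.3%, 79.3%, 81.4% and 90.8% for r = 0, 0.1, 0.2, 0.3 and 0.52.

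**Imbalance-triggered adjustment.** The plan gives no threshold, so three were assumed: one covariate, entered only if its baseline comparison has p below the trigger, 40,000 runs per cell. Ranges are for r = 0.2 to 0.52. Disagreement means that the triggered and unadjusted tests fall on opposite sides of 0.005, per continuous outcome.

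| Trigger | Power, d = 0.40 | Disagreement, d = 0.40 | Disagreement, d = 0.50 |
|---|---|---|---|
| p < 0.05 | 77–79% | 0.7–1.7% | 0.2–0.9% |
| p < 0.10 | 78–80% | 1.2–3.1% | 0.4–1.4% |
| p < 0.20 | 77–81% | 2.0–5.3% | 0.7–2.1% |

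If the trait were always included, its result would disagree with the unadjusted one in 5–15% of trials at d = 0.40.

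A separate five-covariate simulation always included the first covariate (standing for age) and added the others if imbalanced at p < 0.05. At d = 0.40 and R² = 0.30, power was 77% unadjusted, 81% imbalance-selected and 92% with the fixed set.

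**Type I error.** In that simulation the fixed model's error under the null was 0.0048 to 0.0049. Only if either result were allowed to count would per-outcome error rise, to about 0.006 (unadjusted or imbalance-selected) or 0.007 to 0.008 (unadjusted or fixed). The plan does not say that either may count.

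**The case against.** The strongest reply is that little is at stake at the plan's own effect size. Section 17.0 uses d = 0.50 and describes its effect sizes as among the smallest seen in the pilot. Net of cost, the gain there is about 0, 0.6, 1.7 and 4.2 points at r = 0.1, 0.2, 0.3 and 0.52. This stands; the d = 0.40 figures are an illustration.

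The largest gain also rests on an unsupported correlation. The value 0.52 is the midpoint of 0.65 and 0.39, which Section 17.0 uses as a hypothetical Aim 2 power scenario, not as observed data. The pilot text links these traits to negative emotion, distress and social withdrawal, and internalized weight bias to self-regulation failure. It reports no such link for delay discounting, comfort eating, self-efficacy, intentions or cortisol. For outcomes with r of about 0.11 or less there is no gain or a slight loss. This stands too.

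The triggers are assumed, and the plan only allows adjustment without prescribing a rule. So the triggered figures show what such a rule would do; they do not reproduce the plan.

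Finally, the wording leans towards the unadjusted ANOVA, which is valid in a 1:1 randomised design and does not depend on survey items that participants may skip. Both results will be shown, and Aim 2 does use the traits, though not in the test at 0.005. These points limit the weight of the concern. They do not supply a named decisive test, and they do not make imbalance a good criterion for choosing covariates.

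**Conclusion.** The concern holds as a modest improvement worth considering. For covariates beyond age, possible imbalance is the only stated criterion, and the result judged at 0.005 must be inferred. Fixed adjustment for four pre-session covariates would move power at d = 0.40 from 77.3% to between 76.6% and 90.8% for r = 0 to 0.52, and at d = 0.50 from 94.9% to between 94.6% and 99.1%. The benefit is small if r is 0.2 or less, or if the true effect is 0.50 or larger.

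These figures assume two-sided tests, complete data, and continuous outcomes with linear covariate effects. They do not carry over directly to social withdrawal, which the Section 6.0 script records as a choice among three options. The validity of the trial and its familywise error control as written are not in question.

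**What to change.** In Section 17.0, name one confirmatory test per outcome at 0.005, adjusted for a fixed set of pre-session covariates expected to predict the outcomes, regardless of observed imbalance. Age, sex/gender, internalized weight bias and neuroticism are a reasonable example. Use ANCOVA for continuous outcomes, and a categorical-outcome model with the same covariates for the three-option social withdrawal choice. Label the unadjusted result supportive and delete the imbalance criterion. Extend the planned imputation, now described only for missing outcomes, to skipped covariate items.

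The cost is one paragraph, a rule for skipped items, and four of 318 degrees of freedom (about 1.3% of variance if the covariates predict nothing). No new data are needed, because the example covariates are already in the screening or baseline survey. The baseline saliva sample is taken in the lab, so it lies outside a pre-session set. It and the assay-related factors that Section 4.0 leaves to be controlled if needed could be settled in the same paragraph.

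If the team prefers the unadjusted ANOVA as decisive, one sentence should say so and label all adjusted results supportive. That settles the tie-break but forgoes the precision.

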6.0 Procedures Involved

Describe and explain the study design.

The study uses a between-subjects experimental design. Participants will be randomly assigned to one of two conditions: experimental vs. control.

Research procedures, including procedures being performed to monitor subjects for safety or minimize risks.

The study involves two parts: a pre-session online baseline survey and an experimental session that will take place in the lab. Trained research assistants will guide participants through study procedures in the lab, including delivery of the intervention (manipulation), assessment of study outcomes, and study debriefing.

As identified in our pilot data and previous research,^{5,7-9,46,113} employment is a common setting for weight discrimination. Negative employment outcomes (e.g., lower wages, fewer opportunities for promotion) often stem from negative stereotypes that cast employees with obesity as lazy, unintelligent, and incompetent.^{5,8} To manipulate weight discrimination, this study will adapt manipulations widely used in previous experimental studies of social exclusion (conducted by Co-I [name])^{50,112} and weight stigma,⁴¹ as well as our own pilot work.⁴⁸

The study will be presented as an investigation of "decision making in the workplace," during which participants (adults with obesity) will "interact with" and receive initial impression ratings from three "co-workers" ("confederates," that is, research assistants posing as other participants). Participants will be told that the research team has partnered with the FSU marketing department to study how psychological factors affect decision making and that during the lab session they will work with their groupmates to develop a food product marketing campaign.

To begin, participants will create a 3-minute introductory "getting to know you" (GTKY) video, as in our pilot study.⁴⁸ To guide the creation of their video, participants will be provided with a list of "getting to know you" questions (please see attached video introduction questions) they can answer in their video. Participants will also complete a "getting to know you" questionnaire in which they will be asked to indicate their personal qualities (filler questions that assess self-monitoring practices) and social values where they will be asked to rate their attitudes toward elderly adults, overweight people, and

PROTOCOL TITLE: Decision Making Study

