racial and ethnic minority individuals. Participants' videos and "getting to know you" questionnaire responses (averaged across the three members) will (ostensibly) be shown to their group members, and participants will view three similar videos created (ostensibly) by each of their group members. (Please see two sample confederate videos that were uploaded to IRB staff member [name]'s NiFTy account). After watching the videos, participants will provide impression ratings of each group member.

Participants will also be informed that, for the next portion of the session, the group will be divided into pairs to perform a taste-test task and develop ideas for the marketing campaign. Pairs will (ostensibly) be based on each person's preferences for whom they most want to work with based on the initial videos, and participants will be asked to indicate their preferences. The experimenter will say the following:

"For the marketing task we want to partner people with someone they'd like to work with. Things work better that way. So please indicate here on this paper (at the bottom of the 'First Impressions Questionnaire' page 2) which one of your group mates (A, B, or C) you would most like to work with so we can try to partner you with them."

As described in Section 5.0 (Study Intervention), participants will be randomly assigned to one of two manipulations. In the experimental (weight discrimination) condition, participants will learn that their group members are biased against overweight people but not elderly or racial/ethnic minority individuals, as indicated by the GTKY summary ratings handout in which the three member's ratings will be presented in averaged form (experimental condition). Participants will also receive negative feedback about their personal attributes by being labeled with negative weight-based stereotypes (as indicated by the first impressions summary ratings averaged across the three members; experimental condition). Although some ratings will be positive (e.g., they will receive high ratings on being friendly and kind), participants will be rated poorly on attributes viewed as necessary to develop a strong marketing campaign (i.e., motivation to work hard, possessing self-discipline to persist at the task, and competence).

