In the control condition, participants will learn that their group members have positive attitudes toward people with higher body weight, as well as elderly and racial/ethnic minority individuals, as indicated by the GTKY summary ratings handout (control condition). Participants will also receive positive feedback about their personal attributes, as indicated by the summary ratings averaged across the three members (control condition).

After (ostensibly) assembling the group's preferences, the experimenter will inform participants in the experimental condition that no one selected them to be their partner, thus they will perform the next few tasks alone. This manipulation has been shown to prompt feelings of social exclusion.⁵⁰ In contrast, participants in the control condition will be told that one of their group members had to leave unexpectedly for a family emergency, so pairs cannot be assembled as usual, thus they will perform the next few tasks alone. In sum, while participants in both conditions will perform the tasks alone, only those in the experimental condition should experience social exclusion. For the exact wording of the social exclusion manipulation, please see the attached script (social exclusion manipulation).

PROTOCOL TITLE: Decision Making Study

After the manipulation has been delivered, participants will complete a manipulation check (see lab survey). Participants will be asked to indicate their overall impressions of their groupmates and their perception of their groupmates' overall impressions of themselves. Participants will be also report the extent to which they think the impressions their group members formed of them thus far are based on various factors including their gender, race or ethnicity, weight, age, personality, and what they said in their video.⁴⁸

Next, participants will complete primary outcome measures (Table 1). To assess comfort eating, participants will take part in a well-validated faux taste test from previous research (described below).¹⁰² To provide a measure of social avoidance/withdrawal, we will use a previously validated measure⁵⁰ in which participants indicate the extent to which they prefer to complete the final task either by themselves, with a member of their previous group, or with a new partner (described below). Anthropometric measures (i.e., height, weight, waist and hip circumference) will be assessed at the end of the study following standard lab-based procedures.

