To assess cortisol (a steroid hormone that regulates the body's response to stress), participants will be asked to provide three saliva samples during the lab visit. The first saliva sample will be collected at baseline (5-10 minutes after they arrive at the lab). The second and third saliva samples will be collected 25 and 60 minutes, respectively, after delivery of the experimental manipulation. If participants finish all study measures before it is time to collect the third saliva sample, they will be asked to watch a video about marketing strategies to presumably help them prepare for the final task. Here's a link to the kind of video that will be shown to participants:

https://www.youtube.com/watch?v=0Ty64auIk_w

The experimenter will be instructed to stop the video when it's time to collect the sample.

We will use off-the-shelf foods for the taste test task. The following foods/drinks will be offered to participants: Lay's classic potato chips, Chips Ahoy cookies, milk chocolate M&M candies, and Sprite. During the taste test, participants will be provided with plentiful quantities of each food item (i.e., 80 grams of chips, 15 cookies, 300 grams of M&Ms) and 2 (355 mL) can of Sprite. These quantities were selected to circumvent both ceiling effects (i.e., participants eating all of the food available) and floor effects (i.e., participants eating no food at all) and are currently being used in a similar study being conducted by Co-I, [name]. All food items will be stored according to package instructions (e.g., in airtight containers to preserve freshness). Cans of Sprite will be refrigerated. Participants will not be given food items that have become stale or are beyond their "best by" date. Any expired foods will be discarded. For sanitary reasons, any food or drink that is leftover after the taste test will be discarded as soon as the research assistant has logged the post-task weight for each item.

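### Baseline cortisol is part of the AUCg outcome but is not named as a covariate, and no cortisol analysis is designated as deciding; always adjusting for it costs one degree of freedom and gains precision

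*Combined protocol and SAP*

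**What the plan says.** Section 6.0 fixes the timing of the first sample: "The first saliva sample will be collected at baseline (5-10 minutes after they arrive at the lab"), which is before the manipulation. Two further samples follow the manipulation, the last at 60 minutes. Section 17.0 (Aim 1) reduces the three values to one outcome: "we will calculate the area under the curve (AUC) with respect to ground (AUCg").

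The same section plans an unadjusted ANOVA and then covariance and regression models that allow "adjustment for age and other baseline characteristics that may exhibit imbalance across experimental conditions". Age is the only covariate named. On reporting it says "Effect of experimental weight discrimination will be reported for both unadjusted and adjusted analyses", without saying which result decides. Section 4.0 lists factors that may affect the assay, such as food, alcohol, nicotine and medication, recorded "so that we can control for them in analyses if needed". The baseline cortisol level is not among them.

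Cortisol is one of the nine Table 1 outcomes. Section 6.0 places these after the manipulation: "Next, participants will complete primary outcome measures (Table 1"). Cortisol is the only one for which the documents describe a measurement before the manipulation.

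**The concern.** Under this plan baseline cortisol can enter the model only as an unnamed further characteristic, and only if it happens to look imbalanced. Imbalance is the wrong trigger. The gain from a covariate comes from its correlation with the outcome, and AUCg guarantees some correlation here because baseline is one of its terms. In perfectly balanced arms, leaving baseline out still puts all of its variance into the error term.

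Two things are at stake. The first is precision on the only physiological outcome, which is tested at alpha 0.005. The second is an open choice: an unadjusted and an adjusted estimate will both be reported, they can differ, and the plan does not say which one answers the hypothesis. Neither is a question of bias.

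**Working it through.** **1. The plan's own power figure.** Inputs from section 17.0: 160 per arm, d = 0.50, alpha = 0.005. Two-sided testing is assumed, because Aim 1 does not state it. The noncentrality is 0.50 × √(160/2) = 4.472 and the critical t on 318 df is 2.827, which gives power of 94.9%. The plan states 90%. Its figure is conservative: 90% power is reached at d = 0.460. If d = 0.50 is read on AUCg, there is no shortfall.

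**2. Weight of baseline in AUCg.** Let L be the minutes from the baseline sample to the manipulation, and t the time of the second sample. By the trapezoid rule, the weights of the three samples are

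(L + t)/2, (L + 60)/2, (60 − t)/2, each divided by (L + 60).

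The documents do not give L but they bound it:

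- Lower bound, about 9 minutes. The participant's own video is short ("To begin, participants will create a 3-minute introductory") and later "participants will view three similar videos created (ostensibly) by each of their group members". Reading those also as 3 minutes each gives 3 × 3 = 9.
- Upper bound, 55 minutes. The lab visit is 120 minutes (section 9.0), baseline is no earlier than 5 minutes after arrival, and the last sample is 60 minutes after the manipulation: 120 − 5 − 60 = 55.

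The baseline weight then runs from (29/2)/69 = 0.210 (L = 9, t = 20) to (80/2)/115 = 0.348 (L = 55, t = 25). The middle sample always has weight 0.5.

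**3. Variance left after adjustment.** The share left is 1 − corr(AUCg, baseline)². The documents give neither the between-sample correlation r nor the SDs, so both are assumptions. A worked case with L = 30, t = 25 and equal SDs has weights 0.306, 0.500 and 0.194:

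- r = 0: corr² = 0.0934 / (0.0934 + 0.2500 + 0.0378) = 0.245, so 0.755 is left.
- r = 0.5: covariance with baseline = 0.306 + 0.5 × 0.694 = 0.653; variance of AUCg = 0.5 × 0.381 + 0.5 = 0.691; corr² = 0.426 / 0.691 = 0.617, so 0.383 is left.

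Over L = 9 to 55 and t = 20 or 25:

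| Assumption | Variance left | Smallest AUCg effect with 90% power (unadjusted SDs) |
|---|---|---|
| No adjustment | 100% | 0.460 |
| Equal SDs, r = 0 | 69-88% | 0.383-0.432 |
| Equal SDs, r = 0.3 | 49-65% | 0.321-0.370 |
| Equal SDs, r = 0.5 | 35-47% | 0.272-0.315 |
| Unequal SDs, r = 0 | 64-94% | 0.369-0.446 |
| Unequal SDs, r = 0.5 | 32-53% | 0.261-0.334 |

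The last column is 0.460 × √(share left). The unequal-SD rows set the second and third SDs, relative to baseline, at 1.25/1.1, 1.5/1.25 and 0.9/0.8. Unequal correlations of 0.4 (baseline-second), 0.3 (baseline-third) and 0.6 (second-third), with equal SDs, leave 46-63%.

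**4. Cost.** Error df fall from 318 to 317, and the critical t moves from 2.82676 to 2.82682. The covariate pays for itself once its correlation with AUCg exceeds about 0.06. The least favourable row above (94% left) implies a correlation of √0.06 = 0.24. In simulated null trials with L = 30 and t = 25, the ratios of estimator variances were 0.747 (r = 0) and 0.375 (r = 0.5), close to the formula. Type I error at nominal 0.005 was 0.0033-0.0053, with a Monte Carlo standard error of 0.0011. A log-transformed AUCg with log baseline gave much the same ratios, 0.764 and 0.384.

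**5. How far the two estimates can differ.** The SD of (adjusted minus unadjusted), in unadjusted standard errors, is √(1 − share left). With equal SDs this runs from √(1 − 0.883) = 0.34 at r = 0 to √(1 − 0.348) = 0.81 at r = 0.5. That is enough to move a result across 0.005.

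**6. The 20 versus 25 minute conflict.** Moving t from 20 to 25 raises the baseline weight by 2.5/(L + 60): 3.6 percentage points at L = 9 and 2.2 at L = 55.

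**The case against.** The strongest reply is that nothing in the plan is wrong. The unadjusted comparison of AUCg is unbiased under randomisation, it fits a hypothesis about cortisol secretion, and it exceeds its stated power. An adjusted analysis is already planned and baseline cortisol is not excluded from it. The order of analyses, and a power statement without covariates, could be read as making the unadjusted test the deciding one. The absence of a designated analysis applies to all nine outcomes, not just cortisol. The size of the gain rests on correlations and SDs that are not in the documents, and in the least favourable case it is small: with 94% of the variance left, the detectable effect moves only from 0.460 to 0.446, and power at d = 0.50 from 94.9% to 96.2%. The timing bounds are also loose, since they leave no time for debriefing at one end or for questionnaires at the other.

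Most of this stands as a limit on severity and on any claim about size. It does not remove the point. Permission tied to imbalance is not prespecification, and the order of analyses is only a hint. A gain appears in every scenario examined. The margin at d = 0.50 does not carry over to smaller effects: at d = 0.30 unadjusted power is 44%, against 51-65% adjusted at r = 0 and 86-96% at r = 0.5 (equal SDs). One part of the objection should shape the fix: naming baseline cortisol alone still leaves open whether age and the assay factors enter the primary model.

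**Conclusion.** The point holds. Baseline cortisol is a component of the outcome, is already collected, and is not named as a covariate; neither the unadjusted nor the adjusted analysis is designated as deciding. This is a matter of precision and prespecification, not validity, and there is no shortfall against the stated power.

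The direction of the gain is secure across the assumptions examined. Its size is not: the variance removed ranges from 6% to 68%, depending on assumed SDs, on between-sample correlations from 0 to 0.5, and on a baseline-to-manipulation interval of 9-55 minutes. The change should be made because it costs almost nothing. The conflict over the second sample time is real but separate, and its effect on the weights is small.

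**What to change.** In section 17.0, Aim 1:

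- State that the primary cortisol analysis compares AUCg between arms with baseline cortisol always included as a covariate, whatever the observed imbalance.
- If AUCg is transformed, put baseline on the same scale.
- State whether age and the assay factors in section 4.0 also enter this model, so that its covariate set is fixed in advance.
- Report the unadjusted result alongside, as already planned.

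Separately, reconcile the 20-minute (section 4.0) and 25-minute (section 6.0) times of the second saliva sample, since the AUC is built from these intervals.

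The cost is SAP wording and one error degree of freedom (318 to 317) for the baseline covariate. No new data are needed and AUCg is kept. A participant without a baseline sample has no observed AUCg in any case, so the covariate excludes nobody further.
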